Evidence that these biomarkers are mediators of pregnancy outcomes that are affected by smoking has important implications for other pharmacotherapy studies in pregnant smokers by providing surrogate measures of potential risk [46] or in studies of reduced-exposure products (e.g., e-cigarettes, smokeless tobacco) that may be used by pregnant women. Since the FDA has recently been authorized to regulate tobacco products [56] there is likely to be heightened interest in biomarkers of tobacco product risk, particularly in vulnerable populations.

3. Hypotheses, aims and objectives:

Hypothesis 1:

We hypothesize that the nicotine inhaler compared to placebo inhaler will double the 7-day point prevalence abstinence rates (confirmed by exhaled CO) at 32-34 weeks gestation and will reduce the number of cigarettes smoked per day (CPD).

Aims / objectives 1:

To examine the efficacy of the nicotine inhaler compared to a matched placebo for smoking cessation and reduction among pregnant smokers.

Hypothesis 2:

- a) The nicotine inhaler will yield lower cotinine concentrations than placebo at 32-34 weeks gestation.
- b) Infants born to mothers in the NRT group will have higher birth weights and greater gestational age than infants born to mothers randomized to placebo. 2c) Fewer nicotine-treated subjects will deliver a low birth weight (<2500 grams) or a preterm (<37 weeks) infant than those in the placebo group.

Aim/Objective 2:

To compare the nicotine inhaler with placebo on safety measures which include a) overall nicotine exposure (i.e., serum cotinine) and b) birth outcomes (i.e., birth weight and gestational age).

Hypothesis 3: Pregnant women who are heavier smokers (i.e., ≥ 10 cigarettes/day) will be less able to quit with behavioral treatment alone than lighter smokers and the inhaler will increase cigarette abstinence more in heavier smokers.

Aim/Objective 3: To identify factors that determine which women benefit most from the use of nicotine inhaler for smoking cessation during pregnancy

Hypothesis 4: We hypothesize that birth weight will be negatively correlated with CPD and exhaled CO at the end of pregnancy, and that smoking cessation or reduction in the third trimester will explain the effect of treatment group on birth weight. We will also explore the interrelations among birth outcomes, tobacco exposure, and other promising biomarkers.

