Specific Aim 2.a: To compare effects of the nicotine inhaler with placebo on overall nicotine exposure (i.e., measured as serum cotinine), and birth outcomes [i.e., birth weight, gestational age, % of subjects who deliver a LBW (<2500 g) or preterm (<37 wk gestation) infant]. We will use a linear mixed model (see above) to determine whether cotinine concentration changes differentially over time by treatment group.

Specific Aim 2.b: Birth Outcomes. Mean birth weight will be compared for treatment groups using a two-sample t-test, or analysis of covariance if necessary to adjust for imbalances in patient characteristics. We will also compare the percentage of subjects in each group who deliver an infant of LBW (1500-2500 g) or preterm delivery using chi square or logistical regression.

Specific Aim 3: To determine which subjects benefit most from NRT, we will use logistic regression to examine the following predictors of treatment response (i.e., smoking cessation at 6 or 32 wks

Nicotine Replacement for Smoking Cessation during Pregnancy

gestation): pretreatment CPD, FTND score, perceived stress, motivation to quit, self-efficacy, treatment group, and the interaction of treatment group and the other independent (i.e., potential moderator) variables. **Analyses:** First, we will use a stepwise procedure to choose predictor variables and interaction terms that are significant ($\alpha=0.05$). A significant interaction between treatment group and other variables (e.g., pretreatment CPD) implies that the regression coefficients for this variable are not homogeneous with respect to the efficacy of the medication. The Johnson-Neyman procedure [79], which yields values of the continuous moderator variable at which the treatment groups differ significantly on the dependent variable, will be used to determine the “break point” nicotine inhaler efficacy. In our completed study[1], the effect of nicotine gum appeared to depend on CPD during the pretreatment period. For light smokers, the cessation rates were 18% and 21% for the control and nicotine groups, respectively, while for heavy smokers the rates were 0% and 15%, respectively. Since a similar effect in a sample of 150 women would provide power=0.80, using a two-sided $\alpha=0.05$, our proposed sample of 360 pregnant smokers will provide more than adequate power to detect the effect.

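### Aim 3 gives no guaranteed, error-controlled test or estimate of the CPD-by-treatment interaction in Hypothesis 3, because stepwise selection decides which terms are analysed

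*Combined protocol and SAP*

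**What the plan says.** Under Hypotheses, aims and objectives, Hypothesis 3 has two parts. The first is "Pregnant women who are heavier smokers (i.e., ≥ 10 cigarettes/day) will be less able to quit with behavioral treatment alone than lighter smokers". The second is that "the inhaler will increase cigarette abstinence more in heavier smokers". The aim attached to it is wider: to find the factors that mark out the women who benefit most.

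Under Sample size and justification, the Aim 3 power statement concerns CPD alone. It uses rates from the previous gum trial. In the lighter stratum, "For light smokers, the cessation rates were 18% and 21% for the control and nicotine groups, respectively". The contrast drawn with the heavier stratum is that "for heavy smokers the rates were 0% and 15%, respectively". It claims power of 0.80 with 150 women and more than enough with 360. Only Aim 4 is called exploratory.

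Under Method(s) of data analysis, Specific Aim 3, the outcome is "smoking cessation at 6 or 32 wks" and the candidates are "pretreatment CPD, FTND score, perceived stress, motivation to quit, self-efficacy, treatment group, and the interaction of treatment group and the other independent" variables. Then "we will use a stepwise procedure to choose predictor variables and interaction terms that are significant", with alpha 0.05. CPD appears in the interpretation sentence only as an example. The Johnson-Neyman procedure then locates a break point on a continuous moderator.

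No text forces treatment, CPD or their interaction into the model, sets a hierarchy rule, adjusts for multiplicity, names the stepwise variant, or chooses between the two time points.

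**The concern.** The hypothesis and the power statement ask one question, but the analysis makes the answer depend on data-driven selection. Three things can go wrong.

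- The hypothesised interaction may not be selected. The plan then calls for no estimate or interval for it.
- Interactions with no real basis may be selected, because several are screened at 0.05 each, at two time points.
- A term kept because it was significant has, on average, an exaggerated coefficient. That coefficient feeds the Johnson-Neyman break point.

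At stake is the trial's statement about which women gain most from the inhaler.

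**Working it through.** **Inputs from the plan.** N = 360, 1:1. Candidate terms: 1 treatment + 5 moderators + 5 interactions = 11. Alpha 0.05 per term. Two time points. Quit rates, control/nicotine: light 18/21%, heavy 0/15%. For the case of no moderation: 14.9/26.9% (Aim 1).

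**Assumptions, because the plan is silent.** Heavy smokers 30–70% of the sample; all 360 analysed; CPD split at 10 and the other moderators standard normal, correlation 0 or 0.3; latent correlation between time points 0.5 or 0.8; likelihood-ratio (LR) entry and removal at 0.05; no hierarchy rule.

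**Step 1: the plan's own figure.** The stated 0.80 at N = 150 was not reproduced by any two-sided interaction test tried:

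- risk-difference contrast: 0.16–0.20
- LR interaction test: 0.44–0.76
- Wald logit test with a 0.5 correction: 0.05–0.28

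A test in heavy smokers only gives 0.47–0.84, but that is not an interaction test. This is a separate matter, and the conclusion here does not rest on it.

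**Step 2: false moderators when none exist.** Nominal rate for five independent tests:

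- one time point: 1 − 0.95^5 = 0.226
- two independent time points: 1 − 0.95^10 = 0.401

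Simulated stepwise regression (3,000 runs per setting) selected at least one false interaction in 20–23% of trials at one time point and 34–39% at either. A second simulation gave about 26% at one time point. The visit lists and schedule name no instrument for perceived stress. With four moderators the nominal rates are 1 − 0.95^4 = 0.185 and 1 − 0.95^8 = 0.337.

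**Step 3: keeping the CPD interaction when it is real.** N = 360, 1,500 runs per setting, centred product terms:

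| Heavy share | 30% | 50% | 70% |
|---|---|---|---|
| Plan's rates: prespecified LR test, power | 0.96 | 0.998 | 0.997 |
| Plan's rates: stepwise keeps CPD-by-treatment | 0.64 | 0.88 | 0.93 |
| Heavy control rate 5% (assumed): prespecified LR test, power | 0.28 | 0.34 | 0.34 |
| Heavy control rate 5% (assumed): stepwise keeps the term | 0.15 | 0.22 | 0.24 |

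In these trials an interaction for some other variable also entered in 17–20%.

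**Step 4: dependence on the variant.** A second stepwise simulation at the plan's rates kept the CPD term in about 88–95% of trials, but with both main effects also in the model in only 6–10%. A product term without its main effects is not a proper interaction test. The coding of the product term, which the plan does not give, drives this: with plain 0/1 products the main effects usually stay out, and with centred products they usually come in. At the 5% heavy control rate, the second simulation showed no consistent loss against a fixed test.

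**Step 5: the inference method matters too.** At N = 360 the LR power of 0.96 to above 0.99 depends on the 0% heavy control cell. With the corrected Wald test it is 0.37–0.87. On the risk-difference scale, half heavy (90 per cell):

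- contrast = (0.15 − 0) − (0.21 − 0.18) = 0.12
- SE = √[(0.18×0.82 + 0.21×0.79 + 0.15×0.85 + 0)/90] = 0.070
- power = Φ(0.12/0.070 − 1.96) ≈ 0.40

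Over heavy shares of 30–70% that power is 0.31–0.42.

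**The case against.** A reader might infer that Aim 3 does not test Hypothesis 3 at all. The documents do not support that. Pretreatment CPD and its treatment interaction are named candidates, screened at 0.05, and CPD is the plan's own example. At the plan's rates the term survives selection in most simulated trials.

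Nor is CPD the only moderator named in advance. Five are listed, and CPD is the one that is hypothesised. Screening several also fits the plural wording of the aim, which is broader than Hypothesis 3 and is not the main outcome.

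Some of the harm is inferred from silence. Many stepwise routines can enforce hierarchy, so interactions without main effects are possible, not planned. Selecting terms is not the same as suppressing the rest, and nothing says that unselected terms go unreported. No text says that the result would settle who should use the inhaler.

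These points limit the claim but do not remove it. Being a candidate is not the same as having an assured test, and nothing in the text supplies one. A defence that the whole of Aim 3 is exploratory is also unavailable, since the sample-size section reserves that word for Aim 4 and gives Aim 3 a power claim.

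**Conclusion.** The point stands in this form: Aim 3 has no guaranteed, error-controlled test or estimate of the CPD-by-treatment interaction that Hypothesis 3 states.

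The firmest figure is the false-selection rate: about one trial in four or five at a single time point and more than one in three over both, in line with simple arithmetic. The loss of the true CPD term is less certain. At the plan's rates it ranges from about 5% to 36% of trials (retention 64–95%), against about 4% or less for one prespecified LR test. It depends on the assumed heavy share and the unstated stepwise variant. It would be wrong to infer that the term will usually be lost: that appears only under weaker effects, such as an assumed 5% heavy control rate, where the prespecified test is itself underpowered at 0.28–0.34. Exaggeration of selected coefficients is certain in direction, but its size has not been established.

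This concerns a non-primary aim. It should be corrected, and the correction is cheap.

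**What to change.** Replace the stepwise procedure with one prespecified logistic model for cessation at 32–34 weeks, with treatment, CPD and CPD-by-treatment forced in.

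- **CPD scale.** Use the cut at 10 from Hypothesis 3, which is also a randomisation balancing factor, for the test. Use continuous CPD for Johnson-Neyman only, and apply that procedure to no other moderator.
- **Inference.** Name likelihood-ratio or penalised (Firth) inference in advance, because the heavy-smoker control cell may be empty or nearly so.
- **Reporting.** Give the interaction with its 95% confidence interval whatever its p-value. Give the CPD effect within the placebo arm for the first part of Hypothesis 3, which has no stated analysis now.
- **Other moderators.** Analyse them one at a time with main effects retained, Holm-adjusted and labelled exploratory.
- **6-week outcome.** Make it secondary.

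The cost is analysis text only, with no new data, visits or participants. Fewer exploratory moderators will reach significance, and the 6-week result becomes supportive.

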Behavioral treatments during pregnancy are consistently but only modestly effective in helping pregnant women quit smoking [2, 21]. A recent meta-analysis of studies of augmented psychosocial interventions of at least 3 minutes duration (e.g., discussing the risks of smoking and benefits of cessation, providing self-help materials) that used biochemical verification of abstinence [2] showed mean cessation rates of 13.3% in the intervention group and 7.6% in the usual care group [2]. Similarly, a meta-analysis of 64 randomized and quasi-randomized trials (with a total of 28,000 subjects) [21] showed a significantly greater reduction of risk in the intervention groups (RR = 0.94; 95% CI = 0.93-0.95), such that 6% more women quit with a behavioral intervention than with usual care.

Despite their potential value for smoking cessation, augmented behavioral interventions are least effective in heavier smokers [22]. The estimated quit rate for behavioral counseling is 20% in women who smoke <10 CPD, while women who smoke 10-19 CPD have a 15% quit rate, and women who smoke >20 CPD have only a 5% chance of quitting [22]. Moreover, the majority of pregnant smokers, even light smokers, do not quit smoking during pregnancy, even with augmented behavioral interventions [21].

In summary, smoking has serious health risks for the mother and infant, and robust efforts are needed to help pregnant women quit smoking. Most women do not quit smoking during pregnancy, this is particularly true for women with less education and heavier smokers. Behavioral interventions have a modest, but consistent, beneficial effect on quitting, but are least effective in heavier smokers.

A.2. Addressing a Critical Barrier to Progress in the Field: Evaluating the utility of medications for pregnant smokers is important because current best practice treatments help only a small minority of

Nicotine Replacement for Smoking Cessation during Pregnancy

pregnant women to quit smoking. Women who continue to smoke after learning of their pregnancy and of the risks to the fetus may be more dependent smokers who are less able to quit with a behavioral intervention alone [22]. Indeed, one survey shows that pregnant women report nicotine withdrawal symptoms and cravings as major reasons for their inability to quit smoking during pregnancy [23].

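### Aim 3 reads the inhaler's efficacy break point from a Johnson-Neyman significance boundary, which moves with sample size and does not mark where the inhaler starts to work

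*Combined protocol and SAP*

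**What the plan says.** Aim/Objective 3 is stated as "To identify factors that determine which women benefit most from the use of nicotine inhaler". Hypothesis 3 expects a larger increase in abstinence among women smoking 10 or more CPD.

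Under Method(s) of data analysis, Specific Aim 3, the steps come in this order:

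1. The model: "we will use logistic regression to examine the following predictors of treatment response". The candidates are pretreatment CPD, FTND score, perceived stress, motivation to quit and self-efficacy, each with its interaction with treatment group.
2. Selection: "First, we will use a stepwise procedure to choose predictor variables and interaction terms that are significant", at alpha 0.05.
3. Interpretation: "A significant interaction between treatment group and other variables (e.g., pretreatment CPD) implies that the regression coefficients for this variable are not homogeneous".
4. Johnson-Neyman. The plan describes it as a method that "yields values of the continuous moderator variable at which the treatment groups differ significantly on the dependent variable". The same sentence then gives its purpose, that the method "will be used to determine the “break point” nicotine inhaler efficacy".

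For Aim 3 the plan specifies no treatment effect with an interval across the moderator, no interval for the break point and no absolute-difference scale. A risk difference with a 95% confidence interval is specified, but only for Aim 1.

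**The concern.** The plan defines the procedure correctly, as finding where the groups differ significantly, and then gives the result a different meaning. Where a difference becomes significant depends on the effect and on its standard error, and the standard error depends on how many women are enrolled and how their CPD values are spread. A logistic model with a linear treatment-by-CPD term makes the effect change smoothly, so it contains no point at which the inhaler starts to work. The nearest thing to one is the CPD at which the fitted effect is zero, and that is not what the procedure returns.

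A reported CPD cut-off invites the reading that women below it gain nothing. At N=360 it may show only that the interval at those CPD values still includes zero.

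A second, lesser matter is scale. Which women benefit most is naturally a question about extra women abstinent, whereas the logistic interaction compares odds ratios. The two can differ when placebo quit rates vary with CPD, and section A.1 says counseling quit rates do: "The estimated quit rate for behavioral counseling is 20% in women who smoke <10 CPD", against 15% at 10-19 CPD and 5% above 20 CPD.

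**Working it through.** **Plan figures.** The plan gives no number for the break point, so there is none to reproduce. The odds ratio of 2.1 used below comes from Sample size and justification, Aim 1, and is consistent with the rates there: 0.149/0.851 = 0.175; 0.175 × 2.1 = 0.368; 0.368/1.368 = 26.9%.

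**Why the boundary depends on N.** Let b1 be the treatment coefficient, b3 the treatment-by-CPD coefficient and V their covariance matrix. The boundary is the x that solves

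(b1 + b3·x)² = 1.96² × (V11 + 2x·V13 + x²·V33).

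The entries of V shrink as 1/N. With b1 and b3 fixed, the right side goes to zero and the roots move toward −b1/b3. At any finite N the boundary is displaced from that point by sampling error.

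**Check 1: benefit at every eligible CPD.** Assumptions, none of them from the documents:

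- CPD = 5 + gamma(shape 1.6, scale 3.2), median about 9. The lower limit of 5 is the inclusion criterion.
- Placebo logit = −1.4 − 0.07(CPD − 5).
- Log odds ratio = 0.19 + 0.09(CPD − 5), which is 1.21 at 5 CPD and 1.90 at 10. It reaches zero at 5 − 0.19/0.09 = 2.9 CPD, below the entry minimum, so every eligible woman benefits.

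Median lower limit of the region where the inhaler is significantly better, in trials whose interaction is significant at 0.05:

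| N | Median boundary (CPD) |
|---|---|
| 360 | about 9.5 |
| 720 | about 8.25 |
| 1440 | about 7.25 |
| 2880 | about 6.25 |

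At N=360 about 23% of trials have a significant interaction and so reach this step.

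Take a woman at 8 CPD. Her log odds ratio is 0.19 + 0.09 × 3 = 0.46, an odds ratio of 1.58. Her placebo logit is −1.4 − 0.21 = −1.61, or 16.7%. On the inhaler it is −1.15, or 24.0%, a gain of about 7 points. She falls below the median boundary at 360 and 720 and above it at 1440 and 2880, with the same true effect throughout.

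**Check 2: anchored to the earlier gum trial's rates.** The plan reports "For light smokers, the cessation rates were 18% and 21% for the control and nicotine groups, respectively", and 0% and 15% for heavy smokers. Assume the light rates apply at 7 CPD and the heavy rates at 14 CPD, with 2% in place of 0% because 0% has no logit, and CPD from 5 to 25 with mean about 9. The true effect is then zero at 6.3 CPD. Boundaries from the expected information:

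| N | Boundary (CPD) |
|---|---|
| 150 | none |
| 360 | 8.9 |
| 720 | 7.9 |
| 1000 | 7.6 |
| 2000 | 7.2 |
| 5000 | 6.9 |

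At 8 CPD the assumed odds ratio is 1.6, yet at N=360 she lies below the boundary. With the heavy placebo rate at 1-2%, and the heavy CPD value and CPD spread varied, the N=360 boundary runs from 8.5 to 9.9 (at 9.9 the expected interaction misses significance). At a 5% heavy placebo rate the expected interaction is not significant at N=360. At N=2000 all settings give 7.2 to 7.8.

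**Check 3: scale.** Apply a constant odds ratio of 2.1 to the section A.1 rates, with odds = p/(1 − p) × 2.1 and risk = odds/(1 + odds):

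| Counseling rate | Odds × 2.1 | Risk with inhaler | Gain |
|---|---|---|---|
| 20% | 0.525 | 34.4% | 14.4 points |
| 15% | 0.371 | 27.0% | 12.0 points |
| 5% | 0.111 | 10.0% | 5.0 points |

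The logistic interaction is exactly null, while the gain differs nearly threefold between the extreme strata.

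**The case against.** **The plan has a first step.** Stepwise selection comes before Johnson-Neyman, and an interaction dropped there leaves nothing to feed the procedure. The text does not say that Johnson-Neyman runs only after a significant interaction, but that is the natural reading. This stands, and it rules out a stronger claim that a reader might infer, namely that the method would often report a threshold where none exists. Run regardless of the interaction, it flags some value from 5 to 20 CPD in about 12% of trials with no effect, and puts a boundary inside the CPD range in about 85% of trials with a constant odds ratio of 2.1. With a significant interaction required first, these fall to about 4% and 5%, roughly nominal for one moderator. Five independent moderators could give 1 − 0.95⁵ = 23%, but that is a separate question of multiplicity. The first step does not stop the movement with N; the first table already applies it.

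**Mis-ranking is not shown.** A reader might infer that the logistic scale will rank women wrongly. The only within-trial moderation data in the documents rank heavy smokers first on both scales: 3 points and an odds ratio of 1.2 in light smokers, against 15 points and an infinite odds ratio in heavy smokers. The nearly threefold gap in the third check also rests on women above 20 CPD, who are about 3% of the assumed distribution. In addition, no difference at a given CPD is the same null on either scale, so scale bears on the interaction test and the ranking more than on the boundary.

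**Consequences.** Nothing in the documents says that women below the boundary will be told they do not benefit. Johnson-Neyman is also a legitimate descriptive tool. Both points stand; the fault is confined to what the boundary is said to mean.

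**Conclusion.** The point holds, at low severity. The plan takes a significance boundary as the break point of efficacy, and that boundary moves with sample size for a fixed true effect even after a significant interaction is required: about 9.5 CPD at the planned 360, down to about 6.25 at 2880, in a setting where every eligible woman benefits. The dependence on N follows from the definition. The particular CPD values rest on an assumed CPD distribution, placebo slope and effect slope, because the documents give no CPD distribution for this trial.

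The documents do not support saying that the plan will commonly invent thresholds or will mis-rank who benefits. The scale issue is a possibility that the plan leaves open. The primary comparison is untouched.

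**What to change.** In Specific Aim 3:

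- Drop the reading of the Johnson-Neyman boundary as a break point of efficacy. If the boundary is reported, label it the region of significance at this sample size.
- Keep the logistic model. Base the answer on who benefits most on the estimated treatment effect across CPD with a 95% confidence band (simultaneous preferred, though a clearly labelled pointwise band would already cure the main fault), shown as a risk difference and as an odds ratio.
- Add the risk difference with 95% confidence interval below and at or above 10 CPD, the cut already used in the urn randomization and in Hypothesis 3. Present it as a prespecified reporting split and not as a threshold found in the data.
- Do the same for any other continuous moderator that is carried forward.

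The cost is a change of SAP wording, a plot and a short table. No new data are needed. A simultaneous band is wider than a pointwise one, so statements about particular CPD values will be less sharp.

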Aim 3: In our completed study, the effect of nicotine gum appeared to depend on cigarettes per day during the pretreatment period. For light smokers, the cessation rates were 18% and 21% for the control and nicotine groups, respectively, while for heavy smokers the rates were 0% and 15%, respectively. Since a similar effect in a sample of 150 women would provide power=0.80, using a two-sided $\alpha=0.05$, our proposed sample of 360 pregnant smokers will provide more than adequate power to detect the effect.

Aim 4: is exploratory and no sample size was calculated.

Explain on what basis it is reasonable to assume that the sample size will be obtained:

Recruitment will take place over 39 months, requiring enrollment of approximately 9 subjects per month. In our previous study, we had an on-site recruiter at each site (Baystate and Hartford Hospital) and were able to screen 3 pregnant smokers and enroll 2 subjects/week (i.e.,1 subject/site). We will also recruit from CHS in Hartford, where we expect to recruit 1 subject/month. Recruitment sites will be provided with materials designed to raise awareness of the study, including posters and brochures to be displayed prominently in all clinic areas. We will also encourage referrals from clinicians in the surrounding areas at each site, and recruit through newspapers and maternity magazines. Based on our history of recruitment, we are confident that we can reach the proposed recruitment goal.

Subject characteristics:

- Age: **at least 16 years of age**
- Ethnicity: **Hispanic and non-Hispanic. All race and ethnic groups will be eligible**
- Gender: **F**
- Other characteristics - (e.g. primary language etc.): **English or Spanish speaking**

Inclusion Criteria:

- a) smoking at least 5 CPD for the preceding 7 days
- b) previous attempt to quit smoking during pregnancy by self report
- c) 13-26 weeks gestation
- d) at least 16 years of age
- e) able to speak English or Spanish;
- f) intent to carry pregnancy to term; and
- g) stable residence

Exclusion criteria:

Nicotine Replacement for Smoking Cessation during Pregnancy

- a) current drug or alcohol abuse or dependence (other than methadone maintenance)
- b) twins or other multiple gestation
- c) unstable psychiatric disorder
- d) unstable medical problems (e.g., pre-eclampsia, threatened abortion, hyperemesis gravidarum)
- e) known congenital abnormality.

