Mediational analyses: Measures of nicotine withdrawal, depressive symptoms, and perceived stress measured at baseline and at each study visit will serve as potential mediators. Specifically, we expect that the nicotine inhaler will result in a greater reduction in nicotine withdrawal symptoms than placebo, and that these variables will partially mediate the effects of treatment. Tests of mediation using the Mplus statistical package [80], which allows for missing data, will provide evidence of a causal link between treatment, the mediator variable(s), and the outcomes.

Specific Aim 4: To explore mechanisms by which the nicotine inhaler increases birth weight and gestational age. Based on the results of our completed study [3] and another NRT trial [7], we anticipate that offspring born to women in the inhaler group will have a higher birth weight and gestational age than those in the placebo group. If NRT increases birth weight, potential mediators of this effect will be explored. Measures of tobacco use (cigarettes per day, and exhaled CO) and 7 day point prevalence abstinence at each study visit will serve as potential mediators. Specifically, we expect that the nicotine inhaler will result in cessation or a greater reduction in CPD or exhaled CO, and that these variables will partially mediate an increase in birth weight. We will use a Mplus statistical package to perform mediational analyses [80]. The same analytic approach will be used separately to examine gestational age (in wk).

Depending on whether smoking cessation or reduction mediates the effect of NRT on birth weight, the appropriate variable will be used a predictor variable in an additional mediational model that examines potential biomarkers (**C-reactive protein or sICAM**) as mediators of birth weight or gestational age. Specifically we will test with Mplus statistical software whether cessation (or reduction) influences a change in biomarker concentration and whether this increases birth weight or gestational age.

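### The mediation tests are said to show a causal link, but the mediators are not randomised and the plan states no confounder adjustment, time order or sensitivity analysis for them

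*Combined protocol and SAP*

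**What the plan says.** All the relevant text is under Method(s) of data analysis in the combined protocol and SAP, unless noted.

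- **Mediational analyses**, after Specific Aim 3: "Measures of nicotine withdrawal, depressive symptoms, and perceived stress measured at baseline and at each study visit will serve as potential mediators". The Mplus tests on these variables "will provide evidence of a causal link between treatment, the mediator variable(s), and the outcomes". This sentence is not qualified and is not labelled exploratory.
- **Specific Aim 4**: "Measures of tobacco use (cigarettes per day, and exhaled CO) and 7 day point prevalence abstinence at each study visit will serve as potential mediators". The step is conditional: "If NRT increases birth weight, potential mediators of this effect will be explored". A further model, again conditional on the preceding result, tests "whether cessation (or reduction) influences a change in biomarker concentration and whether this increases birth weight or gestational age", with C-reactive protein and sICAM as the biomarkers.
- **Hypotheses, aims and objectives**, Hypothesis 4, expects that "smoking cessation or reduction in the third trimester will explain the effect of treatment group on birth weight".
- **Sample size and justification** says that Aim 4 "is exploratory and no sample size was calculated".

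Randomisation (Baseline, Randomization assignment) covers treatment only. Adjustment is mentioned for arm imbalance in the efficacy and birth-weight comparisons, and baseline predictors enter the Aim 3 moderator regression. No covariates are named for the mediation models. The nearest thing is a statement that cotinine effects will be examined separately from tobacco reduction.

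**The concern.** Randomisation protects the effect of treatment on the mediator and of treatment on the outcome. It does not protect the effect of the mediator on the outcome. A variable that drives both can produce a significant mediator-outcome path with no causal effect behind it, even when the arms are perfectly balanced, so adjusting for arm imbalance does not help.

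The protocol itself points to candidates. Its background says that more dependent women are less likely to quit. It also reports that, in an earlier trial, a difference in serious adverse events, most often preterm delivery, was no longer significant after adjustment for preterm history.

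Time order is also open. Mediators taken at every visit include the visit at which cessation is assessed, and abstinence can itself change withdrawal.

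At stake are the mechanistic conclusions. The biomarker section (A.3) suggests that mediating biomarkers could serve as surrogate measures of risk in other studies. In the biomarker model the predictor is cessation or reduction rather than treatment, so neither path is randomised.

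**Working it through.** **Background figure.** The plan gives no figure for the mediation analyses. Its Aim 1 power is used only to anchor the quit rates. With 180 per arm and 14.9% vs 26.9%, the mean rate is 0.209 and

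z = [0.12 × √180 − 1.96 × √(2 × 0.209 × 0.791)] / √(0.149 × 0.851 + 0.269 × 0.731) = (1.610 − 1.127) / 0.569 = 0.849.

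Power is Φ(0.849) = 0.802, which matches the stated 0.80.

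**Set-up.** The true mediator-to-outcome effect is zero. Treatment shifts the mediator by d standard deviations. A pre-randomisation shared cause gives a mediator-outcome partial correlation r. Mediation is declared when both paths have two-sided p < 0.05 (joint significance). From the documents: N = 360 and the quit rates. Assumed: d, r and the strength of the shared cause. The only d that can be derived is for abstinence as a mediator: 0.12 / √(0.209 × 0.791) = 0.30.

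**Continuous outcome.**

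- Treatment path: Pa = Φ(d√N/2 − 1.96) + Φ(−d√N/2 − 1.96). For d = 0.2, 0.3, 0.4: 0.475, 0.812, 0.967.
- Mediator path: Pb = Φ(atanh(r)√(N−3) − 1.96) + Φ(−atanh(r)√(N−3) − 1.96). For r = 0, 0.05, 0.1, 0.2, 0.4: 0.050, 0.157, 0.474, 0.969, 1.000.
- False-mediation rate ≈ Pa × Pb:

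| | r = 0 | r = 0.05 | r = 0.1 | r = 0.2 | r = 0.4 |
|---|---|---|---|---|---|
| d = 0.2 | 2.4% | 7.5% | 22.5% | 46.0% | 47.5% |
| d = 0.3 | 4.1% | 12.8% | 38.5% | 78.7% | 81.2% |
| d = 0.4 | 4.8% | 15.2% | 45.9% | 93.7% | 96.7% |

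If the shared cause correlates equally (c) with mediator and outcome, r = c². So r = 0.05 to 0.1 needs c of about 0.22 to 0.32, and r = 0.2 to 0.4 needs c of about 0.45 to 0.63. With 75% of the data (the Incentives paragraph's figure for the previous trial), N = 0.75 × 360 = 270. The rate at d = 0.3, r = 0.1 to 0.2 is then about 26% to 63%.

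**Binary quit outcome.** This is the closer match to the causal sentence, which follows the Aim 3 cessation analysis. Simulation: 2,000 trials per scenario, N = 360, linear mediator model, logistic outcome model, quit rates as above.

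| Shared cause (correlation with mediator; log-odds ratio for quitting) | d = 0.2 | d = 0.3 | d = 0.5 |
|---|---|---|---|
| none | 2.4% | 3.7% | 5.0% |
| modest (0.3; 0.3) | 4.8% | 8.2% | 10.4% |
| moderate (0.5; 0.5) | 22.0% | 36.1% | 44.1% |
| strong (0.5; 0.7) | 33.8% | 54.9% | 70.7% |

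The Sobel test gives lower rates: 6.7%, 16.2% and 34.7% for moderate confounding; 14.2%, 30.1% and 60.9% for strong.

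**Two limits.** With the shared cause in both models, the binary rate is at most 5.2% in every scenario. If treatment does not move the mediator (d = 0), the rate stays at or below about 5% whatever the confounding. That second limit does not carry over to the biomarker model, where the predictor is not treatment.

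**Timing.** Entry is allowed to 26 weeks. Baseline is about one week later (27), the quit date within the next week (up to 28), and Visit 5 six weeks after that (about 34, ±10 days). Visit 6 is at 32-34 weeks. For late entrants, Visit 5 is therefore not reliably earlier than Visit 6, and a visit number does not fix the time order.

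**The case against.** A reader might infer that false mediation is likely to be declared. The documents do not support that. They give no size for the confounding and none for the treatment effect on withdrawal, mood or stress, and rates above 90% need both a clear mediator shift and strong confounding. Analysing change from baseline in the mediator may also remove part of the confounding. This stands, so only a labelled range is given.

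A reader might also infer that the plan rules out adjustment. It does not; it is silent.

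Aim 4 is labelled exploratory and conditional on a birth-weight effect. That gate matters. At d = 0.4 and r = 0.2, with no real treatment effect on birth weight, it cuts the rate from about 94% to under 3%. With a real effect of 0.2 SD the rate is about 45%. Near 0.5 SD (the prior trial's 300/607 g) the gate gives little protection. The label and gate do soften the point for Aim 4. Neither covers the causal sentence, which belongs to the withdrawal, mood and stress analysis.

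Finally, it is tempting to argue that women who deliver before Visit 6 lack third-trimester mediators, which would bias the gestational-age model. The number affected is not known, mediators are also measured earlier, and the plan notes that Mplus allows for missing data. This is not pressed as a separate defect.

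**Conclusion.** The point holds in a limited form. The plan claims causal evidence that its stated analysis cannot deliver, because the mediator-outcome path is neither randomised nor adjusted, and time order is not required. The false-mediation rate is not controlled at 5% and may be much higher.

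Under the assumptions above, for a continuous outcome, it is about 7.5% to 22.5% at d = 0.2 with r = 0.05 to 0.1, about 38% to 79% at d = 0.3 with r = 0.1 to 0.2, and about 94% to 97% at d = 0.4 with r = 0.2 to 0.4. For the binary quit outcome it is about 5% to 71%, from modest to strong confounding. These are illustrations, not predictions for this trial.

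The consequence is confined to mechanistic conclusions. The Aim 1 efficacy comparison does not depend on it, so this is a desirable improvement rather than a threat to the main result.

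**What to change.** 1. Pre-specify baseline covariates in both the mediator and the outcome models, from those already collected: CPD, FTND, exhaled CO, PHQ, self-efficacy, motivation to quit, partner smoking, prior preterm delivery and gestational age at entry.
2. Use only mediators measured before the outcome. For gestational age, select mediator measurements by gestational week, not visit number.
3. Add a sensitivity analysis for unmeasured mediator-outcome confounding, since adjustment removes only what is measured.
4. Replace the causal wording with *consistent with mediation (exploratory)*, and apply the same terms to the Aim 4 and biomarker models.
5. While editing, align the mediator list with the assessment schedule, which has the PHQ at only some visits and lists no perceived-stress measure.

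Items 1 to 4 need SAP text and slightly more analysis, with no new data and no added burden on participants. The price is a weaker stated claim.
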